12.7.2 Serious Adverse Events

An SAE is any untoward medical occurrence, in the view of either the Investigator or Sponsor, that:

- results in death,
- is life-threatening,
- results in inpatient hospitalization or prolongation of existing hospitalization,
- results in persistent or significant disability/incapacity, and/or
- is a congenital anomaly/birth defect.

Other important medical events that may not be immediately life-threatening or result in death or hospitalization, based upon appropriate medical judgment, are considered SAEs if they are thought to jeopardize the subject and/or require medical or surgical intervention to prevent one of the outcomes defining an SAE. Serious AEs are critically important for the identification of significant safety problems; therefore, it is important to take into account both the Investigator's and the Sponsor's assessment. If either the Sponsor or the Investigator believes that an event is serious, the event must be considered serious and evaluated by the Sponsor for expedited reporting.

12.7.3 Serious Adverse Event Reporting

An SAE occurring from the time informed consent is obtained, during the study, or within 3 months of stopping the treatment must be reported to the [REDACTED] Safety and Pharmacovigilance group and will be communicated to the Sponsor. Any such SAE due to any cause, whether or not related to the investigational product, must be reported within 24 hours of occurrence or when the Investigator becomes aware of the event. Notification can be made using the dedicated fax line or email [REDACTED] Safety and Pharmacovigilance group:

[REDACTED]
[REDACTED]
[REDACTED]
[REDACTED]
[REDACTED]
[REDACTED]

If the Investigator contacts the [REDACTED] Safety and Pharmacovigilance group by telephone, then a written report must follow within 24 hours and is to include a full description of the event and sequelae in the format detailed in the SAE reporting form.

The event must also be recorded on the standard AE eCRF. Preliminary reports of SAEs must be followed up by detailed descriptions later on, including clear and anonymized photocopies of hospital case reports, consultant reports, autopsy reports, and other documents when requested and applicable. SAE reports must be made whether or not the Investigator considers the event to be related to the investigational drug.

Appropriate remedial measures should be taken to treat the SAE, and the response should be recorded. Clinical, laboratory, and diagnostic measures should be employed as needed in order to determine the etiology of the problem. The Investigator must report all additional follow-up evaluations to the [REDACTED] Safety and Pharmacovigilance group within 24 hours of becoming aware of the additional information or as soon as is practicable. All SAEs will be followed up until the Investigator and Sponsor agree the event is satisfactorily resolved.

Any SAE that is not resolved by the end of the study or upon discontinuation of the subject's participation in the study is to be followed up until it either resolves, stabilizes, returns to baseline values (if a baseline value is available), or is shown to not be attributable to the investigational product or procedures.

12.7.4 Suspected Unexpected Serious Adverse Reactions

Adverse events that meet all of the following criteria will be classified as suspected unexpected serious adverse reactions (SUSARs) and reported to the appropriate regulatory authorities in accordance with applicable regulatory requirements for expedited reporting:

- serious
- unexpected (i.e., the event is not consistent with the safety information in the IB)
- there is at least a reasonable possibility that there is a causal relationship between the event and the study treatment

The Investigator will assess whether an event is causally related to study treatment. The Sponsor [REDACTED] will consider the Investigator's assessment and determine whether the event meets the criteria for being reportable as a 7-day or 15-day safety report. Suspected unexpected serious adverse reactions (SUSARs) that are fatal or life-threatening must be reported to the regulatory authorities and the independent ethics committee (IEC)/institutional review boards (IRBs) (where required) within 7 days after the Sponsor [REDACTED] has first knowledge of them, with a follow-up report submitted within a further 8 calendar days. Other SUSARs must be reported to the relevant regulatory authorities and the IEC/IRBs within 15 calendar days after the Sponsor [REDACTED] first has knowledge of them.

The Sponsor [REDACTED] is responsible for reporting SUSARs and any other events required to be reported in an expedited manner to the regulatory authorities and for informing Investigators of reportable events, in compliance with applicable regulatory requirements within specific timeframes. Investigators will notify the relevant IEC/IRBs of reportable events within the applicable timeframes.

12.7.5 Pregnancy

Women of childbearing potential (WOCBP) must have a negative pregnancy test at Screening [REDACTED]. Following administration of investigational product, any known cases of pregnancy in female subjects will be reported until the subject completes or withdraws from the study. The pregnancy will be reported immediately by faxing/emailing a completed pregnancy report to the Sponsor (or designee) within 24 hours of knowledge of the event. The pregnancy will not be processed as an SAE; however, the Investigator will follow up with the subject until completion of the pregnancy and must assess the outcome in the shortest possible time but not more than 30 days after completion of the pregnancy. The Investigator should notify the Sponsor (or designee) of the pregnancy outcome by submitting a follow-up pregnancy report. If the outcome of the pregnancy involved spontaneous or therapeutic abortion (any congenital anomaly detected

in an aborted fetus is to be documented), stillbirth, neonatal death, or congenital anomaly, the Investigator will report the event by faxing/emailing a completed pregnancy report form to the Sponsor (or designee) within 24 hours of knowledge of the event.

If the Investigator becomes aware of a pregnancy occurring in the female partner of a male subject participating in the study, the pregnancy should be reported to the Sponsor (or designee) within 24 hours of knowledge of the event. Information regarding the pregnancy must only be submitted after obtaining written consent from the pregnant partner. The Investigator will arrange counseling for the pregnant partner by a specialist to discuss the risks of continuing with the pregnancy and the possible effects on the fetus.

Upon discontinuation from the study, only those procedures that would not expose the subject to undue risk will be performed. The Investigator should also be notified of pregnancy occurring during the study but confirmed after completion of the study. In the event that a subject is subsequently found to be pregnant after inclusion in the study, any pregnancy will be followed to term, and the status of mother and child will be reported to the Sponsor after delivery.

12.7.6 Overdose

The dose level of LT3001 drug product will be calculated by the Investigator or a qualified designee [REDACTED]. Since drug accumulation is not anticipated due to the short half-life of LT3001 and subjects will only receive LT3001 drug product administered by an Investigator or a qualified designee and under close monitoring, it is anticipated that the risk of overdose or medication error will be low.

Any overdose or medication errors, with or without associated AEs, should be promptly reported by the Investigators or designee to [REDACTED] Safety and Pharmacovigilance (see contact details in [Section 12.7.3](#)). Overdoses and medication errors will be documented as protocol deviations and communicated to the Study Monitor.

No specific therapy for overdose of LT3001 drug product exists. In the event of overdose or medication error, appropriate standard of care therapy for the subject's symptoms and clinical status will be provided.

14 STATISTICAL ANALYSIS

A statistical analysis plan (SAP) will be prepared after the protocol is approved. This document will provide further details regarding the definition of analysis variables and analysis methodology to address all study objectives. The SAP will serve as a compliment to the protocol and supersedes it in case of differences.

The statistical evaluation will be performed using SAS® software version 9.4 or higher (SAS Institute, Cary, NC). All data will be listed, and summary tables will be provided. Summary statistics will be presented by treatment group and overall. For continuous variables, data will be summarized with the number of subjects (N), mean, standard deviation, median, minimum, and maximum by treatment group. For categorical variables, data will be tabulated with the number and proportion of subjects for each category by treatment group.

14.1 Determination of Sample Size

Approximately 24 eligible subjects will be randomized 2:1 to LT3001 drug product or placebo. It is planned to have 24 subjects in the Evaluable Population, after which enrollment will stop.

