7 INVESTIGATIONAL PLAN

7.1 Description of Overall Study Design and Plan

This is a multicenter, double-blind, single-dose, randomized, and placebo-controlled prospective Phase IIa clinical study, designed to evaluate LT3001 drug product versus placebo/control in subjects with AIS.

There is only one dose of LT3001 drug product [REDACTED]. The dose is based on the results from nonclinical studies, the FIH study in healthy human volunteers (LT3001-101), and US FDA recommendations. Approximately 24 eligible subjects will be randomized 2:1 to LT3001 drug product or placebo. Each eligible subject will receive a single dose of LT3001 drug product or placebo within 24 hours after stroke symptoms onset. LT3001 drug product or placebo will be administered via a [REDACTED] IV infusion. The infusion will be stopped if an SAE occurs during infusion.

The participation for each subject is approximately 92 days from the screening visit (Visit 1) to the last visit. The study design is illustrated in [Figure 1](#). The Schedule of Assessments is provided in [Section 10](#).

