8 SELECTION OF STUDY POPULATION

Section 7.1 provides information regarding number of subjects planned to be randomized.

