9.3.1 Method of Study Treatment Assignment

Subjects will be randomly assigned to receive LT3001 drug product or placebo in a ratio of 2:1.

At Screening [REDACTED] will assign a unique subject identification number to the subject known as the Subject Number. This number

will be associated with the subject throughout the study. [REDACTED]

The subjects will be centrally randomized at a study level. The treatment assignment will be determined by a randomization list prepared by the biostatistics group [REDACTED]

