### **3.5. Determination of Sample Size**

Approximately 24 eligible subjects will be randomized 2:1 to LT3001 drug product or placebo. It is planned to have 24 subjects randomized, after which enrollment will stop.

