## **8. Efficacy**

Efficacy analyses will be conducted for the ITT population, evaluable population PP population and safety population. All statistical tests for secondary efficacy endpoints will be two-sided with  $\alpha = 0.05$ .

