## 12. Changes from Analysis Planned in Protocol

- [REDACTED]
- [REDACTED]
- [REDACTED]
- [REDACTED]
- Update definition of PP population from 'The PP population will comprise all ITT subjects who complete study procedures through Day 90 without a major protocol deviation.' to 'The PP population will comprise all ITT subjects who complete study procedures through Day 90 without a major protocol deviation potentially impacting efficacy measurements.'

This document is confidential.

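### Does it matter that the protocol stops enrolment at 24 evaluable subjects and the SAP at 24 randomised?

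*Protocol*

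**What the plan says.** Protocol section 14.1 repeats the planned number randomised and then adds: "It is planned to have 24 subjects in the Evaluable Population, after which enrollment will stop". SAP section 3.5 (V2.0) has the same sentence with a different population: "It is planned to have 24 subjects randomized, after which enrollment will stop".

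Elsewhere both documents give only an approximate number randomised. Protocol section 7.1 says: "Approximately 24 eligible subjects will be randomized 2:1 to LT3001 drug product or placebo". The protocol synopsis and SAP section 3.3 say the same. Protocol section 8 points back to 7.1 for the number: "Section 7.1 provides information regarding number of subjects planned to be randomized".

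SAP section 8 lists the evaluable set beside the others: "Efficacy analyses will be conducted for the ITT population, evaluable population PP population and safety population". Its definition is not visible in the public text, which is a matter of redaction and not a fault in the plan.

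On precedence, Protocol section 14 says that the SAP complements the protocol and "supersedes it in case of differences". The SAP revision history gives a clarification of the sample-size determination as one of two reasons for V2.0. SAP section 12, headed "Changes from Analysis Planned in Protocol", has one readable entry, on the per-protocol definition, and four redacted ones.

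**The concern.** The total number and the point at which enrolment closes are basic design facts, and here the two documents state them differently. If one of the 24 randomised subjects turns out not to be evaluable, the SAP's stopping point has been reached and the protocol's has not. A reader of the study report could then call enrolment complete or short, depending on which sentence is used.

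In a trial this small a single subject counts. With an exact 16:8 split, one subject is 1/24 = 4.2% of the total, 1/16 = 6.3% of the LT3001 arm or 1/8 = 12.5% of the placebo arm. On its face, the protocol promises 24 evaluable subjects and the SAP's rule does not guarantee them.

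**Working it through.** **The plan's own figure.** The visible text gives no power, effect size, event rate or dropout rate, so 24 cannot be derived. Only the allocation can be checked: 24 × 2/3 = 16 and 24 × 1/3 = 8, a whole-number split.

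**How far apart the rules are.** Let k be the number of the 24 randomised who are not evaluable. The SAP rule yields 24 − k evaluable. The protocol sentence needs at least 24 + k randomised.

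| k | Evaluable under the SAP rule | Minimum randomised under the protocol sentence |
|---|---|---|
| 0 | 24 | 24 |
| 1 | 23 | 25 |
| 2 | 22 | 26 |

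**Over an assumed range.** The documents give no non-evaluable share d, so 0 to 20% is an assumption made only to show scale. The number to randomise for an expected 24 evaluable is 24/(1 − d), rounded up. The expected evaluable count from 24 randomised is 24 × (1 − d).

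| d (assumed) | To randomise for 24 evaluable | Expected evaluable from 24 |
|---|---|---|
| 0 | 24 | 24 |
| 5% | 26 | 22.8 |
| 10% | 27 | 21.6 |
| 20% | 30 | 19.2 |

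**What this does to the primary safety question.** The safety set is everyone randomised and dosed (Protocol 14.2, SAP 5.2), so it loses no one through non-evaluability. What the protocol sentence could do is add subjects. Assume that all are dosed and that no LT3001 subject has a symptomatic haemorrhage. The one-sided 95% upper bound on the LT3001 event rate is then 1 − 0.05^(1/n):

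- 24 randomised, n = 16: 17.1%
- 27 randomised, n = 18: 15.3%
- 30 randomised, n = 20: 13.9%

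At an assumed true rate of 5%, the chance of seeing at least one event, 1 − 0.95^n, is 56%, 60% and 64% respectively. A study of any of these sizes describes safety; none can exclude a moderate excess of haemorrhage.

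**What it does to efficacy.** There is no primary efficacy analysis (SAP 8.1). The main efficacy set is ITT (Protocol 14.2, SAP 5.3), which is 24 under the SAP rule whatever k is.

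**Who acts on the sentence.** Protocol section 9.3.1 says: "The subjects will be centrally randomized at a study level". Enrolment need not be closed by each site reading section 14.1 for itself.

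**What the report will show.** SAP section 7.1 already calls for the number and percentage of subjects in each population, so the evaluable count should be visible beside the number randomised under either rule.

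**The case for a change.** The strongest argument for a change is that the precedence clause may not reach this far. It follows a sentence describing the SAP as the place for analysis variables and methods, and a rule for closing enrolment is neither. If the clause does not apply, the protocol sentence is still live and the two documents conflict with no stated tie-break. Aligning them would cost one sentence.

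The doubt about scope stands; the documents do not settle it. But it also weakens any instruction to align the protocol to the SAP. If the clause applies, the 24-evaluable sentence has been superseded and there is no live target to miss. If it does not, there is no clear ground for deleting the protocol's rule in favour of the SAP's. Nor do the other passages decide the matter: an approximate 24 randomised can accommodate 24, or the 25 or 26 needed when one or two subjects are not evaluable, and section 7.1 contains no stopping rule.

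It is also fair to say that the SAP's stopping sentence, unlike the approximate figure, leaves no room for a 25th subject, so the two sentences cannot be read as saying the same thing. That too stands. It does not give the difference any consequence for an analysis.

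Failure to disclose the change cannot be alleged, since the redacted entries in SAP section 12 may already record it.

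**Conclusion.** The two stopping sentences differ, and a careful edit would have made them match. It is a clerical mismatch with no bearing on what the trial does or can conclude. The working rule is probably 24 randomised, because of the precedence clause and the V2.0 revision entry. The remaining doubt is whether that clause covers enrolment as well as analysis.

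Under the SAP rule the only cost is k fewer than 24 in the evaluable set. No stated power or precision figure rests on that set, ITT remains at 24, and safety membership turns on dosing. Had the protocol sentence been followed, the gain over an assumed non-evaluable share of up to 20% would be at most 30 − 24 = 6 more subjects randomised. The zero-event upper bound for LT3001 would be 17.1 − 13.9 = 3.2 percentage points lower. These sizes rest on the assumed share, exact 2:1 allocation and full dosing.

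Rewording section 14.1 would gain nothing beyond tidiness. The planned disposition summary will show how many were randomised and how many were evaluable, which is what a reader of the report needs.

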14.2 Analysis Populations

Enrolled Population

The enrolled population will include all individuals who sign the ICF.

Intent-to-Treat (ITT) Population

The ITT population will include all subjects who are randomized, irrespective of any deviation from the protocol or premature discontinuation. The treatment group assignment will be designated according to initial randomization. The ITT population will serve as the primary basis for the analysis of efficacy.

Per-Protocol (PP) Population

The PP population will comprise all ITT subjects who complete study procedures through Day 90 without a major protocol deviation. The PP population will also be used for the analysis of efficacy.

Safety Population

The safety population will include all randomized subjects who receive at least 1 dose of investigational product. The treatment group assignment in this population will be defined by the treatment actually received. This population will be used for the analysis of safety.

14.3 Safety Analysis

14.3.1 Analysis of Primary Safety Endpoint

The frequency and proportion of symptomatic intracranial hemorrhage (sICH) within 36 hours of dosing will be reported by treatment group and overall. Comparisons by treatment group will be made [REDACTED]

14.3.2 Analysis of Secondary Safety Endpoints

14.3.2.1 Occurrence of sICH

The frequency and proportion of sICH [REDACTED] will be reported by treatment group and overall. Symptomatic ICH will not be imputed for subjects missing either NIHSS score or CT/MRI examination so the denominator will be the number of subjects in whom sICH could be assessed. Comparisons of treatment group will be made [REDACTED] no formal adjustment for multiple comparisons will be made.

14.3.2.2 Occurrence of Asymptomatic ICH

The frequency and proportion of asymptomatic ICH at each time point will be reported by treatment group and overall. Intracranial hemorrhage will not be imputed for subjects missing either NIHSS score or CT/MRI examination at each visit so the denominator will be the number of subjects in whom ICH could be assessed. Comparisons of treatment group will be made [REDACTED] no formal adjustment for multiple comparisons will be made.

14.3.2.3 Occurrence of Mortality Due to Intracerebral or Other Major Bleeding Complications

The frequency and proportion of subjects who have died due to intracerebral or other major bleeding complications at each time point will be reported by treatment group and overall.

14.3.2.4 Occurrence of Mortality Due to Any Reason

The frequency and proportion of subjects who have died due to any reason will be reported at each time point by treatment group and overall. Comparisons of treatment group will be made [REDACTED] no formal adjustment for multiple comparisons will be made.

14.3.2.5 Proportion of Subjects With an Increase in the NIHSS of ≥ 4 Points

The overall proportion of subjects with an increase in the NIHSS of ≥ 4 points will be presented by treatment group [REDACTED]

14.3.2.6 Other Safety Analyses

All reported AEs will be coded using the current Medical Dictionary for Regulatory Activities (MedDRA) in place at the time of analysis. The incidence of TEAEs within 90 days after dosing, including severity, will be included in incidence tables. The summary tables will include the number of subjects and the number of events. Percentages will be based on the number of subjects. Events with missing onset dates will be included as treatment-emergent. If a subject experiences more than 1 occurrence of the same AE, the occurrence with the greatest severity and the closest association with the investigational product will be used in the summary tables. Serious AEs and AEs causing discontinuation will be tabulated. All AEs will be listed by subject, along with information regarding onset, duration, relationship and severity to investigational product, action taken with investigational product, treatment of event, and outcome.

Clinical laboratory data, vital signs, and 12-lead ECG will be summarized using descriptive statistics, including mean values and mean change from baseline values, as well as numbers of subjects with values outside limits of the normal range at each time point. For laboratory tests, abnormal values will be flagged in the data listings.

Summary tables will be provided for concomitant medications initiated during the study period.

14.4 Efficacy Analyses

14.4.1 Occurrence of Recurrent Stroke [REDACTED]

The frequency and proportion of subjects who have a recurrent stroke within 90 days of dosing will be reported by treatment group and overall.

14.4.3 National Institute of Health Stroke Scale

The NIHSS is a standardized method to measure the level of impairment caused by a stroke and was developed by the National Institutes of Health. The NIHSS allows for objective comparison of efficacy across different treatments for stroke, including rehabilitation interventions.

The NIHSS is a brief and reliable stroke deficit assessment scale composed of 11 components and the numbers of grades for each component vary; however, for each component, a score of 0 is defined as normal while higher scores indicate increasing severity of impairment.

[REDACTED] Data missing on

the visit level will not be imputed, and no statistical inferences will be performed.

The proportion of subjects with NIHSS of 0-2 points will be presented by treatment group [REDACTED]

